1.1 Study design

According to the study protocol, subjects will be allocated to 3 main treatment arms:

- Arm A (subjects with new-onset plaque psoriasis to be treated with secukinumab 300 mg s.c.): composed of Arm A1 (A1a and A1b) and Arm A2
- Arm B1 (subjects with new-onset plaque psoriasis to be treated with narrow band –UVB): composed of Arm B1a and Arm B1b
- Arm C (subjects with chronic plaque psoriasis to be treated with secukinumab 300 mg s.c.): composed of Arm C1 and Arm C2

An overview of the treatment arms is summarized in [Table 1-1](#).

Table 1-1 Summary information for study arms

Arm	Psoriasis duration	Study part	Treatment	Treatment duration
A1a	new-onset	Main	Secukinumab	52 weeks
A1b	new-onset	Main and mechanistic	Secukinumab	52 weeks
A2	new-onset	Mechanistic	Secukinumab	104 weeks
B1a	new-onset	Main	nb-UVB	52 weeks
B1b	new-onset	Main and mechanistic	nb-UVB	52 weeks
C1	Chronic	Mechanistic	Secukinumab	52 weeks
C2	Chronic	Mechanistic	Secukinumab	104 weeks

The design consists of a Main Study and a Mechanistic Sub-study.

The Main Study will be multicenter, randomized, 2-treatment-arm (secukinumab and nb-UVB), parallel-group and open-label. It will include 3 clinical epochs (Screening Phase, Treatment Phase, and Follow-up Phase) involving all subjects in Arms A1 (A1a and A1b) and B1 (B1a and B1b).

The Mechanistic Sub-study will be open-label and comprise 5 treatment arms (A1b, A2, B1b, C1, and C2) comprising of subjects who have agreed to provide biopsy samples for investigation. It will include 2 phases (Screening Phase and Treatment Phase) for subjects in

Arms A2, C1 and C2. Subjects from Arms A1b and B1b will undergo the 3 clinical phases of the Main Study.

Screening Phase

Subject's eligibility for the study will be assessed at the Screening visit (Day -28 to Day -1 before Baseline) and at the Baseline visit.

Main study treatment Phase

At the Baseline Visit (Visit 1), eligible subjects will be randomized to one of the following treatment arms (see [Figure 1-1](#) below):

- **Arm A1:** Subjects with new-onset plaque psoriasis will receive 300-mg secukinumab by s.c. injection at Baseline, Weeks 1, 2, 3, 4 and then every 4 weeks until Week 48, inclusive.

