- **Arm B1:** Subjects with new-onset plaque psoriasis will receive either 1 or 2 cycles of nb-UVB of 12 weeks each with a maximum break of 28 weeks between cycles (subjects with PASI 90 at Week 40 will not receive a second treatment cycle). Only during the first 4 weeks of each cycle, nb-UVB treatment will be given in combination with topical calcipotriol 50 µg/g and betamethasone 0.5 mg/g.

Follow-up Phase

At the end of the Treatment Phase at Week 52, all subjects with \geq PASI 50 response from Arm A1 and Arm B1 will enter the Follow-up Phase. Subjects who do not achieve a PASI 50 response, will have all assessments of end of study (EOS) and be discontinued from the study.

[figure not shown]
During the Follow-up Phase, subjects will not receive study treatment; they will be observed maximally until Week 208, and compared regarding the proportion of them who achieve PASI 90 response at Week 104.

Subjects who relapse (those who experience a loss of 50% of the maximum improvement in PASI score achieved during the Treatment Phase) will have all assessments of EOS and be discontinued from the study.

If no relapse occurs, subjects who achieve $<$ PASI 90 at Week 52 in Arms A1 (A1a and A1b) and B1 (B1a and B1b) will be followed until Week 104, while subjects who achieve \geq PASI 90 at Week 52 will be followed until Week 208.

The investigator should provide ongoing adequate care for subjects who relapse. If the investigator decides to continue treating the subjects with secukinumab, a new loading dose of commercially available secukinumab could be considered. The treatment with secukinumab after relapse will be out of scope of the study.

Figure 1-1 Study design – Main study

BL = baseline, EOS = end of study, KSE = key secondary endpoint, nb-UVB=narrow-band ultraviolet B, PASI = psoriasis area and severity index, PE = primary endpoint, R = randomization.

Mechanistic Sub-study

A separate informed consent will be obtained from study subjects who agree on having skin biopsies taken and therefore become eligible for this Mechanistic Sub-study. Besides the biopsies, subjects will undergo the same assessments as in the Main Study.

Treatment Phase

At the Baseline Visit, eligible subjects will be allocated to one of the treatment arms of the mechanistic Sub-study (see [Figure 1-1](#)):

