2.15.3 Subject disposition

Subject disposition data will be summarized separately for the additional analysis. All tables, figures and listings mentioned in this section will be based on the Follow-up efficacy analysis set.

Subject disposition will be summarized for follow-up phase as described in [Section 2.3.1](#) for the subjects in follow-up efficacy analysis set.

Primary reason for subject discontinued follow-up phase by week 208, Week 52- Week 104, Week 104-Week 152 and Week 152- Week 208 will be summarized by treatment group.

Median time to event (i.e. study discontinued) after Week 52 and quartiles including 95% confidence intervals will be provided. The confidence intervals will be based on log-log transformation (PROC LIFETEST option conftype=log-log). Completers will be treated as censored. An analysis will be followed as :

- Date of event minus date of Week 52 plus 1 day for subjects experiencing the event
OR
- Date of censoring minus date of Week 52 plus 1 day for subjects not experiencing the event

Time from End of Treatment to Week 52:

Duration between Last dose of Treatment to the Analysis visit Week 52 will be analyzed as ; (Treatment end date -Date of Week 52 + 1) . Summary statistics n, mean, median, SD, Min, Max , Q1 and Q3 of duration of end of treatment to Week 52 is analyzed. Number and percentage of subjects will be displayed for the subjects with duration of > 4 weeks, > 8 weeks , > 12 weeks , > 16 weeks and so on. Analysis to be displayed up to the maximum duration between last dose of treatment to the Analysis visit Week 52 for every 4 weeks.

Subjects with missing visit week 52 date will be excluded from analysis of time to discontinuation and time from End of Treatment to Week 52.

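### SAP 2.15.3 subtracts the wrong way round for time from end of treatment to Week 52, so on-schedule gaps come out negative and the > 4 weeks rows are empty

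*SAP*

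**What the plan says.** SAP 2.15.3 (subject disposition for the additional analyses) plans a summary of the time from end of treatment to Week 52 in the follow-up efficacy analysis set.

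- The quantity is introduced with "Duration between Last dose of Treatment to the Analysis visit Week 52 will be analyzed as", and the formula given is "Treatment end date -Date of Week 52 + 1".
- Besides n, mean, median, SD, minimum, maximum and quartiles, the section asks for counts by length of gap: "Number and percentage of subjects will be displayed for the subjects with duration of > 4 weeks, > 8 weeks , > 12 weeks", and so on.
- The range of rows is set by "Analysis to be displayed up to the maximum duration between last dose of treatment to the Analysis visit Week 52 for every 4 weeks".
- Just above, time to discontinuation is defined the other way round, later date first: "Date of event minus date of Week 52 plus 1 day for subjects experiencing the event". The censored case follows the same pattern.

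The schedule behind the variable is in SAP 1.1. Arm A1 is dosed at baseline and Weeks 1 to 4, "then every 4 weeks until Week 48, inclusive". Arm B1 receives one or two "cycles of nb-UVB of 12 weeks each with a maximum break of 28 weeks between cycles", and a subject with PASI 90 at Week 40 gets no second cycle.

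**The concern.** The label describes an elapsed time that starts at the last treatment and ends at the Week 52 visit. Such a time is positive, and the week categories only make sense for positive values. The formula puts the start date first, so it gives the negative of the gap plus one day.

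At stake is one descriptive table with a useful purpose. Time off treatment at Week 52 differs between and within arms by design: about 4 weeks in A1, about 40 weeks in B1 after a single cycle, and close to zero in B1 after a late second cycle. The protocol treats time since cessation as relevant, since Section 9.5.1 plans a supportive analysis of PASI 90 at 52 weeks after treatment stops. A reader of the Week 104 comparison in the follow-up set would look to this table for the difference in gaps, and as written its category rows would not show it.

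**Working it through.** The SAP gives no numerical result for this variable, so there is no figure to reproduce. The check is date arithmetic on the planned schedule.

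**Inputs**
- Day convention: day = 7 × week + 1. This reproduces the scheduled days in SAP Table 2-1: Week 16 = 113, Week 24 = 169, Week 52 = 365.
- Last planned A1 dose: Week 48, so 7 × 48 + 1 = Day 337 (SAP 1.1).
- B1, one cycle: last session at about Week 12, so about Day 85 (assumed from the 12-week cycle).
- B1, two cycles with the longest break: 12 + 28 + 12 = 52 weeks, so the last session can fall at about Day 364 or 365.
- Week 52 analysis window for A1 and B1: Day 310 to 407 (SAP Table 2-1 and footnote).
- First category cut: 4 weeks = 28 days.

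**Formulas.** Let E be the treatment end day, V the day of the Week 52 visit, and G = V - E the true gap.
- As written: W = E - V + 1 = 1 - G.
- Reversed with +1: G + 1. Reversed without +1: G.

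| Case | E | V | As written | Reversed, +1 | Reversed, no +1 |
|---|---|---|---|---|---|
| A1, on schedule | 337 | 365 | -27 | 29 | 28 |
| B1, one cycle | 85 | 365 | -279 | 281 | 280 |
| B1, last session the day before the visit | 364 | 365 | 0 | 2 | 1 |
| B1, last session on the visit day | 365 | 365 | +1 | 1 | 0 |
| A1, visit at end of window | 337 | 407 | -69 | 71 | 70 |
| A1, visit at start of window | 337 | 310 | +28 | -26 | -27 |
| B1, late second cycle, visit at start of window | 364 | 310 | +55 | -53 | -54 |

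**What follows from W = 1 - G**
1. W is negative exactly when G is 2 days or more. It is 0 when G = 1 and +1 when G = 0.
2. W exceeds 28 only if 1 - G > 28, that is, if the last treatment comes at least 28 days after the assigned visit. With the visit on Day 365, none of the scheduled cases gets there, so the > 4 weeks row and all higher rows are empty. The subjects who could enter them are those whose treatment had not yet ended at the visit, such as the +55 case.
3. The mean and median of W are 1 minus the true mean and median. The minimum of W is 1 minus the true maximum, and the lower quartile is 1 minus the true upper quartile; the other end swaps in the same way. n and SD are unchanged.
4. The maximum that sets the number of rows comes from the subject with the shortest time off treatment.
5. Dropping the minus sign afterwards is not a repair: for an on-schedule A1 subject it gives 27, which is neither the gap (28) nor the inclusive count (29).

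**The +1 at the threshold.** A1's scheduled gap is 365 - 337 = 28 days. Without +1 it is 28 and not > 28; with +1 it is 29 and is > 28. The convention alone decides whether every exactly on-schedule A1 subject counts as more than 4 weeks off treatment.

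**The case against.** The strongest reply is that the intent is plain. The heading, the sentence and the positive categories all fix the direction, and a table of negative values with empty rows would be noticed at first output. This is a transposed formula in one descriptive table. The table belongs to analyses that SAP 2.15 says were added at the Week 104 analysis, beyond the protocol, and it covers only the follow-up efficacy set. SAP 2.4.1 separately summarises sessions per cycle, exposure by cycle and the number needing a second cycle. All of this stands and limits the weight of the point. It does not make the written rule correct, and a programmer who silently reverses the sign still has to decide on the +1.

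Four stronger readings are tempting, and the documents do not support them.

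- *Every duration is negative and no subject can enter a > 4 weeks row.* A second nb-UVB cycle may run to about Week 52, giving 0 or +1, and the window opens at Day 310, so an assigned visit can precede the last treatment and give a positive value.
- *The table shows nothing.* n and SD are right, and the other statistics can be recovered by applying 1 minus the printed value and swapping the ends.
- *The +1 is itself an error.* The SAP counts inclusively for study day (2.1.1.2), onset time (2.3.2.2), exposure (2.4.1) and the neighbouring durations in 2.15.3. Keeping or dropping it is a convention.
- *The error touches the Week 52 comparison of the arms.* The primary analysis runs on the FAS and mFAS and does not use this variable, and no passage makes this table the main qualification of that comparison.

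**Conclusion.** The point holds in limited form. The subtraction is reversed relative to the quantity it is meant to measure. On the planned schedule it gives -27 instead of 28 or 29 days in A1, and about -279 instead of 280 or 281 in single-cycle B1. The category rows are then empty, and the mean, median, quartiles and extremes are wrong in sign or order. Off schedule, a subject still under treatment at the assigned visit can be counted as more than 4 weeks off it.

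This rests on three assumptions: treatment end date means the date of last dose or session, as the sentence introducing the formula indicates; a single nb-UVB cycle ends at about Week 12; and scheduled days follow 7 × week + 1. A day's change in the nb-UVB end date does not alter the conclusion.

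The consequence is minor: one descriptive summary in the additional follow-up analysis. No primary or key secondary test, confidence interval or power figure depends on it.

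**What to change.** Replace the definition in SAP 2.15.3 and settle three things in it:

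1. **Direction.** Duration in days = date of the Week 52 analysis visit minus treatment end date.
2. **The +1.** State whether it applies. Without it, on-schedule A1 subjects have 28 days and fall outside > 4 weeks; with it they have 29 and fall inside. Either is defensible. Leaving it out makes the value the elapsed time; keeping it matches the rest of the SAP. If it is kept, a table footnote should say that A1's scheduled gap lies on the cut.
3. **Last treatment after the assigned Week 52 visit.** State how these subjects are shown, for example in a separate row for treatment not ended at the visit. Reversing the subtraction makes their values negative, so they need a rule under either convention.

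The cost is one or two sentences in the SAP and a check of the output program. If the table has already been produced, rerun it and record the correction in the clinical study report, where SAP Section 1 says changes from the SAP are to be described. No new data, model or test is needed.

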2.15.4 Demographics and Baseline characteristics

For the additional analysis , summary statistics (n, mean, median, std, min and max) will be presented for continuous demographic and Baseline characteristic variables at baseline and Week 52 visit by treatment for all subjects in the follow-up efficacy analysis set

Similarly for categorical variables, the number and percentage of subjects in each category will be presented similar to Main study for baseline and Week 52 visit by each treatment arm for all subjects in the follow-up efficacy analysis set.

Age group, weight group and BMI group will be presented for both baseline and Week 52. All other demographic and baseline characteristic categorical variables will be presented only at baseline.

2.15.4.1 Demographics

Age, age categories (18-30, 31-50), weight, weight group, BMI and BMI group variables will be summarized for both baseline and Week 52. Week 52 visit date will be used to calculate subject age at the time of visit at Week 52.

All other variables presented as in Section [2.3.2.1](#) will be summarized only at baseline.

2.15.4.2 Disease history and Baseline characteristics at Visit 1 and Week 52

Disease history and baseline characteristics collected at baseline (Visit 1) will be summarized by treatment for follow-up efficacy analysis set. All variables will be presented as in Section [2.3.2.2](#)

In addition, the following disease characteristics categories will be presented at Week 52:

- PASI total score
- PASI categories (0, > 0-3, > 3-5, > 5)
- PASI response (50-75, >75-90, >90-100)

■

██████████

- IGA mod 2011 score

■

████████████████████

2.15.5 Analysis of PASI 90 response at Week 104

2.15.5.1 Comparison of Secukinumab vs nb-UVB for PASI90 response at Week 104 for follow up efficacy analysis set

[figure not shown]
In the comparison of Secukinumab vs nb-UVB for PASI90 response at Week 104 for Follow-up efficacy analysis set, selection of subjects for PASI90 response at Week 104 will be similar to the [section 2.6.1](#).

2.15.5.2 Statistical hypothesis, model, and method of analysis

For the additional analysis, the same hypothesis testing and method of analysis will be performed as secondary analysis [Section 2.6.2](#). An analysis will be performed only for observed data at week 104.

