Body region	Erythema (E)	Thickening (plaque elevation, induration, I)	Scaling (desquamation, D)	Area score (based on true area %, A) ^a
Head (H) ^b	0 = none	0 = none	0 = none	0 = no involvement
	1 = slight	1 = slight	1 = slight	1 ≥ 0 to < 10%
	2 = moderate	2 = moderate	2 = moderate	2 = 10 to < 30%
	3 = severe	3 = severe	3 = severe	3 = 30 to < 50%
	4 = very severe	4 = very severe	4 = very severe	4 = 50 to < 70%
				5 = 70 to < 90%
				6 = 90-100%
Trunk (T) ^c	0 = none	0 = none	0 = none	0 = no involvement
	1 = slight	1 = slight	1 = slight	1 ≥ 0 to < 10%
	2 = moderate	2 = moderate	2 = moderate	2 = 10 to < 30%
	3 = severe	3 = severe	3 = severe	3 = 30 to < 50%
	4 = very severe	4 = very severe	4 = very severe	4 = 50 to < 70%
				5 = 70 to < 90%
				6 = 90 -100%
Upper limbs (U)	0 = none	0 = none	0 = none	0 = no involvement
	1 = slight	1 = slight	1 = slight	1 ≥ 0 to < 10%
	2 = moderate	2 = moderate	2 = moderate	2 = 10 to < 30%
	3 = severe	3 = severe	3 = severe	3 = 30 to < 50%
	4 = very severe	4 = very severe	4 = very severe	4 = 50 to < 70%
				5 = 70 to < 90%
				6 = 90 -100%
Lower limbs (L) ^d	0 = none	0 = none	0 = none	0 = no involvement
	1 = slight	1 = slight	1 = slight	1 ≥ 0 to < 10%
	2 = moderate	2 = moderate	2 = moderate	2 = 10 to < 30%
	3 = severe	3 = severe	3 = severe	3 = 30 to < 50%
	4 = very severe	4 = very severe	4 = very severe	4 = 50 to < 70%
				5 = 70 to < 90%
				6 = 90 - 100%

a) Percentage (not score) of body region (not whole body) affected will be entered in the eCRF.

b) Neck is assessed as part of the Head (H) body region.

c) Axillae and groin are assessed as part of the Trunk (T) body region.

d) Buttocks are assessed as part of the Lower limbs (L) body region.

Definitions of efficacy variables based on the psoriasis area severity index

The following definitions will be used in this study based on the CHMP guidelines for psoriasis (CHMP/EWP/2454/02):

- **PASI 50-89 response:** patients who achieve \geq PASI 50, but $<$ PASI 90 improvement (reduction) compared with baseline
- **PASI 90 response:** patients achieving \geq 90% improvement (reduction) in PASI score compared to baseline are defined as PASI 90 responders
- **PASI 100 response/remission:** PASI = 0, complete clearance
- **Relapse:** when the achieved maximal PASI improvement from baseline is reduced by \geq 50% (CHMP/EWP/2454/02)

[REDACTED]

[REDACTED]

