2.6.2 Statistical hypothesis, model, and method of analysis

For the key secondary analysis, the following hypothesis testing will be performed:

$$H_{02}: p_{sec}^* = p_{nbUVB}^* \text{ versus } H_{A2}: p_{sec}^* > p_{nbUVB}^*$$

where p_{sec}^* and p_{nbUVB}^* are the proportion of subjects who achieve PASI 90 response at Week 104 in the secukinumab 300 mg s.c. (Arm A1) and nb-UVB (Arm B1) arms respectively. This testing will be performed using an exact logistic regression analysis similar to the primary analysis, with the strategy below under consideration. In case of no covariates is significant, exact logistic regression analysis will be performed using only Treatment as fixed effect factor.

Missing data will be handled similarly as for the primary endpoint analysis. Subjects who relapse will be considered non-responders in addition to those who discontinue the study before Week 104 because of lack of efficacy or AEs.

Testing strategy

Since the primary and the key secondary hypotheses are not mutually independent, an adjustment for multiplicity is considered here to control the alpha level (Type I error) i.e., familywise error rate.

This adjustment will be made using a hierarchical testing procedure which states that first H_{01} will be tested at 1-sided $\alpha=2.5\%$ level of significance. The obtained p-value from the fitted logistic regression model will be divided by 2 and this resultant p-value needs to be considered. If the resultant p-value is smaller than 0.025, H_{01} is rejected at 2.5% significance level, concluding that there is strong evidence to consider that secukinumab is performing better than nb-UVB at Week 52. However, if this resultant p-value is greater than 0.025, H_{01} is not rejected at 2.5% significance level, concluding that the evidence obtained from the observed sample is not strong enough to say that any one of the treatment arms is performing better than the other. "PASI score" eCRF page will be used to get above information.

The testing sequence will continue to test H_{02} at $\alpha=2.5\%$ (1-sided), only if H_{01} is rejected.

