2.6.3 Handling of missing values/censoring/discontinuations

As specified in [Section 2.5.3](#), the method of handling missing responses for the key secondary variable will also be the modified multiple imputation method, similarly as for the primary endpoint analysis. Subjects who relapse (a loss of 50% of the maximum improvement in PASI score) or who do not achieve a PASI 50 response at Week 52, will be considered non-responders in addition to those who discontinue the study before Week 104 because of lack of efficacy or AEs.

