2.15.2 Analysis sets

Two analysis sets will be defined for the additional analysis:

Follow-up Efficacy Analysis Set : Subjects in the mFAS who have at least one PASI assessment after Week 52 up to Week 104, and who have no major protocol deviations based on < PASI50 criteria i.e. Subjects with < PASI50 response at the end of treatment epoch at Week 52 lead to protocol deviations, will be excluded from this analysis set.

Follow-up Safety Analysis Set: Subjects in the mFAS who have at least one safety assessment after Week 52 up to Week 104.

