2.15.5.3 Handling of missing values/censoring/discontinuations

The additional analysis will be performed only for the observed data at Week 104 , hence missing data will not be imputed.

[Redacted]

[Redacted]

[REDACTED]

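### The added Week 104 PASI 90 analysis in the follow-up set does not say whether relapsers who leave before the Week 104 window count as non-responders or drop out of the denominator

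*SAP*

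**What the plan says.** SAP 2.15 adds efficacy comparisons in subjects who entered follow-up. It says that they were prompted by the Week 104 main-study results, go beyond the protocol, use observed data only, and keep the main study's testing criteria. The passages that bear on relapsers are these.

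- **Method.** SAP 2.15.5.2: "the same hypothesis testing and method of analysis will be performed as secondary analysis", with a reference to 2.6.2.
- **Relapse rule in the borrowed method.** SAP 2.6.2: "Subjects who relapse will be considered non-responders in addition to those who discontinue the study before Week 104" for lack of efficacy or AEs. SAP 2.6.3 repeats the rule under its missing-values heading: such subjects "will be considered non-responders in addition to those who discontinue the study before Week 104 because of lack of efficacy or AEs".
- **Data limit.** The next sentence of 2.15.5.2: "An analysis will be performed only for observed data at week 104". SAP 2.15.5.3 adds "hence missing data will not be imputed" and does not mention relapse.
- **Exit.** SAP 1.1: subjects who relapse "will have all assessments of EOS and be discontinued from the study".
- **Set membership.** SAP 2.15.2: "Subjects in the mFAS who have at least one PASI assessment after Week 52 up to Week 104", excluding those below PASI 50 at Week 52.
- **Window.** SAP Table 2-1 puts Week 104 for Arms A1 and B1 at Day 716 to 771.
- **Relapse definition.** Protocol 6.4.1: relapse is "when the achieved maximal PASI improvement from baseline is reduced by" 50% or more.

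Two passages lean the other way. The objective in SAP 2.15.1 refers to all subjects in the set, and 2.15.5.1 sends the reader to 2.6.1 for the selection of subjects.

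**The concern.** A relapser who exits before Day 716 is in the analysis set and has no Week 104 PASI. The borrowed method calls that subject a non-responder; the observed-data limit appears to remove the subject. No visible passage says which rule prevails.

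The choice is not neutral. Subjects removed for relapse are failures at exit by the trial's own definition, so leaving them out removes only non-responders. The result then describes PASI 90 among subjects still on study, in a trial whose stated purpose is longer symptom-free periods. SAP 2.1 puts this analysis in the final study report, where a second one-sided Week 104 test would stand beside the key secondary result with a denominator that the text does not fix.

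**Working it through.** **1. Which reading is likelier.** The relapse rule sits in the missing-data paragraph of 2.6.2 and under the missing-values heading of 2.6.3. Section 2.15.5.3 carries the same heading and replaces the content with no imputation. SAP 2.1 bases percentages on evaluable subjects. Together these favour leaving early relapsers out. The wording of 2.15.1 and the link to 2.6.1 keep the other reading open.

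**2. Status at relapse.** Improvement cannot exceed 100% of baseline PASI. A loss of at least half of the maximum leaves at most 0.5 x 100% = 50%, which is below 90%.

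**3. The protocol's own adjustment (Protocol 9.9).** The rates of 23% v 5%, with 7% v 16% loss counted as non-response, give 0.23 x 0.93 = 0.2139 and 0.05 x 0.84 = 0.042, matching the stated 21% and 4%. Full enumeration of the one-sided Fisher exact test at 0.025 with 80 per arm gives 90.0% power at 21% v 4%, against the stated figure of around 89%.

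**4. Effect of leaving non-responders out.** Let p be the response rate with leavers counted as non-responders, and r the fraction of the arm removed, all non-responders. The observed-case rate is p/(1-r) and the observed-case odds are p/(1-r-p). With q = r/(1-p),

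OR(observed) = OR x (1-qB)/(1-qA).

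This is exact and needs no set size.

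**5. Illustration on the protocol's 7% v 16%.**

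| Quantity | Leavers as non-responders | Leavers removed |
|---|---|---|
| Rates, from rounded 21% v 4% | 21% v 4% | 0.21/0.93 = 22.6% v 0.04/0.84 = 4.8% |
| Odds ratio, rounded | (0.21/0.79)/(0.04/0.96) = 6.38 | (0.21/0.72)/(0.04/0.80) = 5.83 |
| Odds ratio, unrounded 21.39% v 4.2% | 6.21 | 5.68 (the protocol's 23% v 5%) |
| Difference, rounded | 17.0 points | 17.8 points |

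Check: qA = 0.07/0.79 = 0.089 and qB = 0.16/0.96 = 0.167, so the factor is 0.914 and 6.38 x 0.914 = 5.83.

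**6. Equal loss does not cancel when the rates differ.** On 21% v 4%, 16% loss in both arms gives (0.21/0.63)/(0.04/0.80) = 6.67. An assumed 50% in both gives (0.21/0.29)/(0.04/0.46) = 8.33. The risk ratio stays at 5.25.

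**7. Direction depends on the split.** Assumed values of q (A1 v B1): 10% v 20% gives 0.8/0.9 = 0.89; 60% v 50% gives 0.5/0.4 = 1.25. With assumed counts of 17/70 v 3/50, the one-sided Fisher p is 0.006 with relapsers kept. If 50% of A1 and 75% of B1 non-responders are removed (17/44 v 3/15), p is 0.16. If 75% and 50% are removed (17/30 v 3/26), p is 0.0004.

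**8. Date formula in 2.15.3.** The duration from end of treatment to Week 52 is written as treatment end date minus Week 52 date plus 1. With the last A1 dose on Day 337 (48 x 7 + 1) and the visit on Day 365, this gives 337 - 365 + 1 = -27. The intended value is 365 - 337 + 1 = 29.

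**The case against.** Observed-case analysis is a declared choice. SAP 2.15, 2.15.5.2 and 2.15.5.3 each say so, and 2.15 gives it as the reason for adding the analysis. The analysis is labelled as beyond the protocol and prompted by results, and the all-randomised key secondary analysis applies the relapse rule. SAP 2.15.3 tabulates discontinuation reasons by arm for this set. The endpoint in 2.6.1 looks at Week 104 only, so non-response for an early relapser is an assigned value. All of this stands and limits the weight of the point. It does not settle the denominator: declaring observed data does not say whether the relapse rule that comes with the borrowed method survives.

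The contents list of the SAP also names a key secondary model section (5.6.2) and redacted parts of 2.15 that are absent from the public text. If one of them states the status of relapsers, the ambiguity disappears.

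A reader might infer that the added test is biased towards secukinumab. The documents do not support that. In a simulation (20,000 replicates, 20% response in both arms, 70 v 60 subjects, one-sided Fisher test at 0.025), the observed-case test declares A1 superior in 4.3% of trials at 40% v 30% loss and 7.5% at 60% v 50%, but in only 0.7% at 7% v 16%. With relapsers kept it is 1.3-1.6% throughout. Apart from 7% v 16%, every input is assumed, and the larger figures need more relapse on secukinumab. At 60% v 50% loss the observed-case rates also truly differ (0.20/0.40 = 50% v 0.20/0.50 = 40%), so 7.5% is not an error rate for the quantity that analysis estimates.

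A reader might also infer that the Week 104 confirmatory result is compromised. It is not: 2.6.2 and 2.6.3 keep relapsers as non-responders, and this analysis is outside the H01-H02 sequence.

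SAP 2.15.9 limits IGA to observed data in the same way. Relapse is defined on PASI, so the known-failure argument does not carry over directly, and missing counts as non-response for Week 104 IGA on the FAS and mFAS (2.13.4). A change there would be a preference.

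**Conclusion.** The point holds as an unresolved rule in a supportive analysis. The text does not fix whether early relapsers are non-responders or are left out, and the likelier reading leaves out subjects whose failure at exit is known. That raises both rates and moves the odds ratio by (1-qB)/(1-qA).

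Size and direction are unknown, because the documents give no relapse rate for this set. The 7% v 16% figure combines lack of efficacy, AEs and relapse among 80 randomised per arm, so it is not a relapse share here. Used as an illustration, it lowers the odds ratio from about 6.2-6.4 to 5.7-5.8, a small shift against secukinumab. The set is selected after randomisation, so the result is supportive under either reading.

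The reversed subtraction in 2.15.3 is a separate, minor error. It gives negative durations when treatment ends well before the Week 52 visit, so the categories from more than 4 weeks upward would be empty.

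**What to change.** In SAP 2.15.5.3:

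- State that members of the follow-up efficacy analysis set who left before the Week 104 window because of relapse, lack of efficacy or an AE count as Week 104 non-responders, as in 2.6.3. For relapse this matches the known status at exit; for AEs it follows the SAP's convention.
- State that members with no Week 104 value for any other reason stay out of the denominator, in line with the no-imputation rule, and show their number per arm.
- Show the current observed-case result beside it, with the number of relapsers left out per arm.
- Label both results as supportive and post hoc.

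In 2.15.3, correct the formula to (Date of Week 52 - Treatment end date + 1).

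The cost is a re-run of existing programs and lower displayed rates. The rule would also be set after the Week 104 results were known. It is, however, the SAP's own prespecified rule for the key secondary endpoint, and showing both results lets a reader see what the choice does.
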